Participants who meet the eligibility requirements at the Screening visit will be enrolled in the study. To prevent the development of tumor lysis syndrome (TLS), dosing of venetoclax will not commence until the participants have completed 4 weeks of ibrutinib (Cycle 1). Participants will be evaluated for development of tumor lysis syndrome (TLS) on Days 1 and 2 of venetoclax dose escalation days during the lead-in phase (Cycle 2). TLS, however, is an extremely rare occurrence in patients with WM. To err in the side of safety, all patients will receive allopurinol 300 mg PO once daily starting 72 hours prior to first dose of venetoclax and continuing at least to the end of Cycle 2.

Patients will be evaluated for safety on the first day of each cycle (4 weeks \pm 1 week) at cycle 2, and 3 and thereafter every 3 cycles (12 weeks \pm 1 weeks) for the duration of therapy. Patients will also be evaluated for safety at each venetoclax dose escalation. Patients will be evaluated for response after completing 4 weeks of therapy. Response criteria updated at the Sixth International Workshop on Waldenström macroglobulinemia (Owen 2013) will be used to assess response, stable disease, and progressive disease. QOL questionnaire will be administered at Cycles 1, 4, 7, 13, 19, EOT, and every 6 months during follow-up.

The Sponsor-Investigator and other study investigators instructed all participants to undergo cardiac screenings, which included labwork, ECG, and Echocardiograms after 3 events of

ventricular arrhythmia, including 2 fatal, occurred on this study. Consultation with cardiology and cardiac stress tests were advised for some participants.

Study treatment for all participants was terminated by the Sponsor-Investigator in March of 2022 due to 4 events of ventricular arrhythmia. As of 4/1/22 all participants were notified and instructed to stop study treatment and accrual was permanently discontinued. Follow-up will continue for 4 years or until death, per protocol.

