5.5 Criteria for Taking a Participant Off Protocol Therapy

Duration of therapy will depend on individual response, evidence of disease progression and tolerance. In the absence of treatment delays due to adverse event(s), combination treatment may continue for 24 cycles, or until one of the following criteria applies:

- Dose delays of >28 days for either ibrutinib or venetoclax*
- Disease progression
- Intercurrent illness that prevents further administration of treatment
- Unacceptable adverse event(s)
- Participant demonstrates an inability or unwillingness to comply with the oral medication regimen and/or documentation requirements
- Participant decides to withdraw from the protocol therapy
- General or specific changes in the participant's condition render the participant unacceptable for further treatment in the judgment of the treating investigator

*Participants may be continued on protocol therapy at the discretion of the Principal Investigator.

Participants will be removed from the protocol therapy when any of these criteria apply. The reason for removal from protocol therapy, and the date the participant was removed, must be documented in the case report form (CRF). Alternative care options will be discussed with the participant.

Study treatment for all participants was terminated by the Sponsor-Investigator in March of 2022 due to 4 events of ventricular arrhythmia. As of 4/1/22 all participants were notified and instructed to stop study treatment and accrual was permanently discontinued.

When a participant is removed from protocol therapy and/or is off of the study, the participant's status must be updated in OnCore in accordance with REGIST-OP-1.

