5.6 Duration of Follow Up

Participants will be followed for a maximum of 6 years from Cycle 1 Day 1, with 4 years of follow-up or until death, whichever occurs first. Participants removed from protocol therapy for unacceptable adverse event(s) will be followed at a minimum until resolution or stabilization of the adverse event. Participants will be followed for progression free survival until documented disease progression or initiation of new therapy. After this, they will be followed for survival until the conclusion of the follow-up period.

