⁵Coagulation profile. Prothrombin time (PT) will be performed at screening and repeated as clinically indicated. PT will be reported as well as the international normalized ratio (INR) and PTT.

⁶For women of childbearing potential only: Serum pregnancy test is required at screening.

⁷QOLs should be performed at C1, C4, C7, C13, C19, EOT, and every 6 months thereafter through follow-up.

⁸ QOL can be collected via telephone or email

⁹ Physical exam, and weight need to be collected at every other visit starting at Cycle 7 (i.e. C7D1, C13D1, C19D).

¹⁰ Participants will undergo assessments during follow-up until time to progression or new therapy. After PD or new therapy initiation, participants will be followed for survival status only

¹¹ Participants who have experienced disease progression or started new therapy will be followed for survival status only every 6 months (+/- 2 weeks)

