11.1.2 Response Criteria Modified VIth IWWM (NCCN 2014)

Participants may undergo plasmapheresis when clinically indicated. Those who undergo plasmapheresis will be unevaluable for any response assessment for 28 days. If plasmapheresis occurs between screening and Cycle 1 Day 1, the screening serum IgM should be used for response determination.

Complete Response (CR): A complete response (CR) is defined as having resolution of WM related symptoms, normalization of serum IgM levels with complete disappearance of IgM paraprotein by immunofixation, and resolution of any adenopathy or splenomegaly. A complete response requires reconfirmation demonstrating normal serum IgM levels, and absence of IgM paraprotein by immunofixation by a measurement repeated at least 2 weeks later.

Very Good Partial Response (VGPR): is defined as $\geq 90\%$ reduction in serum IgM levels, or normalization of serum IgM levels with persistent IgM monoclonal spike in SPEP or immunofixation.

Partial Response (PR): Partial response (PR) is defined as achieving a $\geq 50\%$ reduction in serum IgM levels.

Minor Response (MR): A minor response (MR) is defined 25-49% reduction in serum IgM levels.

Progressive Disease (PD): Progressive disease (PD) is defined as occurring when a greater than 25% increase in serum IgM level occurs with an absolute increase of at least 500 mg/dL from the lowest attained response value, or progression of clinically significant disease related symptom(s). Reconfirmation of the initial IgM increase is required when IgM is the sole criterion for progressive disease confirmation. Death from any cause or initiation of a new anti-neoplastic therapy will also be considered a progression event. For participants on active therapy who are on an ibrutinib drug hold for > 7 days, serum IgM levels will be considered unevaluable for response assessment. Patient must be on ibrutinib for >2 consecutive weeks to be considered eligible for serum IgM response assessment. An increase of 1 cm in any axis for adenopathy, or 2 cm in the craniocaudal axis of the spleen will be considered evidence of progression of extramedullary disease. Development of Bing Neel syndrome, or other extramedullary disease manifestations, as well as disease transformation will be considered as progressive events.

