11.1.1 Time-to-event definition

- Progression-Free Survival (PFS) is defined as the duration of time from start of treatment to time of objective disease progression (including initiation of new therapy or death). Median, 2-year and 4-year landmark PFS analysis will be determined.
- Overall survival (OS) is defined as the duration of time from start of treatment to time of death or last follow-up. Median, 2-year and 4-year landmark OS analysis will be determined.
- The duration of response (DOR) for a given participant will be defined as the number of days from the day the criteria are met for ORR to the date that PD or death are objectively documented. If a participant is still responding, then the participant's data will be censored at the last study visit at which a tumor assessment was performed.

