13. STATISTICAL CONSIDERATIONS

This is a single-arm open-label Phase II study to evaluate the safety and efficacy of Ibrutinib combined with Venetoclax (IVEN) in symptomatic, treatment naïve WM patients.

Study treatment for all participants was terminated by the Sponsor-Investigator in March of 2022 due to 4 events of ventricular arrhythmia. As of 4/1/22 all participants were notified and instructed to stop study treatment and accrual was permanently discontinued.

13.1 **Study Design/Endpoints**

The primary endpoint of the current study is:

- To evaluate the rate of VGPR or better of the combination Ibrutinib + Venetoclax (IVEN) in participants with symptomatic, treatment naïve WM, within 24 months of therapy.

13.2 **Sample Size, Accrual Rate and Study Duration**

Following a Fleming’s one step approach, and assuming a null (H0) VGPR or better rate of 25% (based on previous experience on single-agent ibrutinib efficacy in previously untreated patients with WM), and an alternative (H1) VGPR rate of 45%, a total of 50 evaluable patients need to be accrued to show the proposed difference with an alpha (2-sided type I error) of 0.03 and a power (1-beta or type II error) of 87%. Assuming 10% drop out or unevaluable rate, up to 55 participants will be enrolled. If 19 or more participants obtain a VGPR then the combination of ibrutinib and venetoclax warrants further evaluation. If fewer than 19 participants obtain a VGPR, the combination should not continue further evaluation.

Accrual Targets					
Ethnic Category	Sex/Gender				
	Females		Males		Total
Hispanic or Latino	2	+	6	=	8
Not Hispanic or Latino	10	+	32	=	42
Ethnic Category: Total of all participants	12 (A1)	+	38 (B1)	=	50 (C1)
Racial Category					
American Indian or Alaskan Native		+		=	
Asian		+	1	=	1
Black or African American	1	+	1	=	2
Native Hawaiian or other Pacific Islander		+		=	
White	11	+	36	=	42
Racial Category: Total of all participants	12 (A2)	+	38 (B2)	=	50(C2)
	(A1 = A2)		(B1 = B2)		(C1 = C2)

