13.6 Analysis of Secondary Endpoints

The secondary endpoints are:

- To evaluate the rates of CR with IVEN in participants with symptomatic treatment naïve WM at 6, 12 and 24 cycles of therapy.
- To evaluate the best overall response to IVEN in participants with symptomatic, treatment naïve WM.
- To evaluate the rate of VGPR at 30 months post treatment initiation. To evaluate median time to response, median time to major response and median time to VGPR to IVEN in participants with symptomatic, treatment naïve WM.
- To evaluate the 24-, 36-, 48-, 60-month Progression Free Survival (PFS) of IVEN in participants with symptomatic treatment naïve WM.
- To evaluate the overall survival of participants treated with IVEN
- To evaluate the time to next treatment with IVEN
- To evaluate the effect of IVEN in the bone marrow burden of disease in participants with symptomatic treatment naïve WM.
- To evaluate the impact of CXCR4 mutations on response to IVEN in participants with symptomatic treatment naïve WM.
- To evaluate the safety profile of IVEN in participants with symptomatic treatment naïve WM.
- To evaluate the impact of IVEN in the participants' QOL.

Continuous variables will be presented as medians and interquartile ranges. Categorical variables will be presented as numbers and proportions. Responses will be defined based on the criteria established by the 6th International Workshop on WM. Secondary outcomes will include the rate of VGPR at 30 months from treatment initiation, and the rate of progression-free survival (PFS) at 24, 36, 48 and 60 months from initiation of study treatment. Overall survival will also be evaluated as a secondary endpoint.

PFS analysis will be performed using the Kaplan-Meier methodology, and participants will be censored at the time of last relevant assessment if they have not demonstrated the event of interest by the end of the study. Interim analyses for safety and efficacy will be performed when 15 patients had completed 6 and 12 months of study treatment.

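### PFS counts any new anti-neoplastic therapy as an event, and after the study-wide treatment stop Section 13.6 plans nothing to separate switches without progression from disease return

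*Combined protocol and SAP*

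**What the plan says.** The event rule appears twice. Section 11.1.2, under progressive disease, says "Death from any cause or initiation of a new anti-neoplastic therapy will also be considered a progression event". The PFS definition (the second section numbered 11.1.1, Time-to-event definition) runs from start of treatment to "time of objective disease progression (including initiation of new therapy or death". Neither text depends on why the new therapy was started.

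Follow-up is built to match. Section 5.6: "Participants will be followed for progression free survival until documented disease progression or initiation of new therapy". Footnote 10 of the study calendar: "After PD or new therapy initiation, participants will be followed for survival status only".

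Section 13.6 specifies Kaplan-Meier estimation. Its censoring rule, applied at study end, reads: "participants will be censored at the time of last relevant assessment if they have not demonstrated the event of interest". PFS is named at 24, 36, 48 and 60 months. Time to next treatment is listed as a separate secondary endpoint.

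On the termination, Section 13 states: "Study treatment for all participants was terminated by the Sponsor-Investigator in March of 2022 due to 4 events of ventricular arrhythmia". Section 1.1 adds: "Follow-up will continue for 4 years or until death, per protocol". For participants removed from protocol therapy, Section 5.5 says: "Alternative care options will be discussed with the participant".

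**The concern.** Scoring new therapy as progression rests on the idea that a new treatment usually signals failing disease. A stop imposed on all participants at once for a cardiac safety signal weakens that link. Anyone still on study drug in March 2022 had not completed the planned 24 cycles. Such a person could move to another agent while still responding and would be recorded as a PFS event on the switch date.

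Because only survival status is collected after that, any later progression goes unrecorded. In a single-arm trial no concurrent group shows how much of the curve reflects disease and how much reflects the stop. The landmark PFS figures could then describe two processes without saying in what proportion.

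**Working it through.** The plan states no PFS target, event count or PFS power, so there is no figure to reproduce. The check sets the texts side by side and then illustrates the size.

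**Reading the texts together**

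1. Event: any new anti-neoplastic therapy, with no condition on the reason (11.1.2 and the PFS definition).
2. Censoring: only participants without the event of interest (13.6). There is no exception for therapy started after the sponsor's stop.
3. Data after the switch: survival status only (5.6 and calendar footnote 10).
4. Stop: all participants, for safety and not for progression (13), with follow-up continuing (1.1).
5. Separation: 13.6 has no breakdown of events by type, no alternative censoring rule and no sensitivity analysis.

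It follows that a participant without progression who starts another agent after the stop is a PFS event on the start date, and that no planned output shows this.

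**Illustration of size**

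Let S be PFS at a landmark if such switches were not events. Let s be the share of otherwise event-free participants who switch without progression before that landmark. With complete follow-up to the landmark, reported PFS = S × (1 − s). Neither S nor s is in the documents.

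With S = 90% (assumed):

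- s = 0%: 0.90 × 1.00 = 90%
- s = 10%: 0.90 × 0.90 = 81%
- s = 20%: 0.90 × 0.80 = 72%
- s = 30%: 0.90 × 0.70 = 63%

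A second version takes its level from the one PFS figure that Section 2.3 gives for previously untreated patients on ibrutinib alone, 92% at 18 months. It assumes a constant hazard, so S(t) = 0.92^(t/18). The figure serves only to set a level and is not a comparator.

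| Month | s = 0% | s = 10% | s = 20% | s = 30% |
|---|---|---|---|---|
| 24 | 89.5% | 80.5% | 71.6% | 62.6% |
| 36 | 84.6% | 76.2% | 67.7% | 59.2% |
| 48 | 80.1% | 72.1% | 64.1% | 56.0% |
| 60 | 75.7% | 68.2% | 60.6% | 53.0% |

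Each 10% of switching costs about 9.0 points at 24 months (0.895 × 0.10) and 7.6 points at 60 months (0.757 × 0.10). In practice s would build up over time, so a single row is more realistic than reading one column down all landmarks.

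**The case against.** The strongest reply is that nothing here is an error. Progression, new therapy or death is an ordinary composite. It is stated the same way in both definitions and matched by the follow-up rules, and it avoids the informative censoring that comes from dropping people when they switch. That stands, and it is why the definition should stay.

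A reader might go further and infer three things that the documents do not support:

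- **That PFS is biased downward.** For the composite as defined, a new-therapy start is the event of interest, so there is no bias. The estimate is lower only relative to a progression-only PFS, which the protocol did not adopt.
- **That such switches happened.** No section reports one. The Section 5.5 sentence on alternative care is general off-therapy wording. The design always planned treatment-free follow-up after at most 24 cycles, so stopping drug does not in itself imply starting another. Some starts would be progression anyway under the symptomatic criterion in 11.1.2.
- **That the results cannot be compared with the ibrutinib PFS figures in Section 2.3.** That section does not say how those studies treated new therapy, so the effect of this rule on comparability cannot be judged. No such comparison is planned.

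It is also fair to say that PFS is secondary and carries no hypothesis test. The primary endpoint of VGPR or better and its 19-responder rule do not use it. Time to next treatment already reports new-therapy starts, and setting those dates against documented progression could identify the switches. But no planned output makes that link for the PFS curve. A supplementary curve has limits too: it cannot recover progression after a switch, and its censoring may be informative.

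**Conclusion.** The point holds as a gap in the analysis plan and not as a contradiction or a wrong definition. When the termination text was added to Section 13, Section 13.6 gained no means of showing how much of PFS comes from new therapy without documented progression.

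The size is unknown and may be nil. Under the assumed 90% PFS, the illustrated range runs from no change at 0% switching to a 27-point difference (90% against 63%) at 30%. This rests on the assumed values of S and s and on complete follow-up to the landmark. The primary conclusion of the trial is unaffected. The change is worth making because it is nearly free and lets a reader of a single-arm trial see what the PFS events are.

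**What to change.** Keep the current PFS definition as the main analysis. Add the following to Section 13.6 before PFS is analysed, stating openly that it was added after the March 2022 stop:

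1. A table of PFS events by type: IgM progression, clinical progression, extramedullary progression or transformation, new therapy without documented progression, and death.
2. A supplementary Kaplan-Meier PFS in which new therapy without documented progression is censored at the last disease assessment before that therapy.
3. A statement that this censoring may be informative, so the two curves are read together, and that the supplementary curve does not recover progression after the switch.

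The cost is a few sentences, one table and one curve. The analysis needs the new-therapy start date and the assessments up to it, but not the reason for switching. Time to next treatment already requires the start date. The study calendar has no row for subsequent therapy, so the team should confirm that the date is captured. If no participant switched without progression, the table will show it and the two curves will coincide.

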3.2 Exclusion Criteria

Participants who exhibit any of the following conditions at screening will not be eligible for admission into the study:

- 3.2.1 Participants who have one or more prior systemic therapies for WM.
- 3.2.2 Participants who are receiving any other investigational agents.
- 3.2.3 Participants with known CNS lymphoma.
- 3.2.4 Participants with known history of Human Immunodeficiency Virus (HIV), chronic hepatitis B virus (HBV) or hepatitis C (HCV) requiring active treatment. Note: Participants with serologic evidence of prior vaccination to HBV (i.e., HBs Ag-, and anti-HBs+ and anti-HBc-) and positive anti-HBc from IVIG may participate.
- 3.2.5 Concurrent administration of medications or foods that are moderate or strong inhibitors or inducers of CYP3A within 7 days prior to first dose of study drug.
- 3.2.6 Participants with chronic liver disease and hepatic impairment meeting Child-Pugh class C (Appendix B).
- 3.2.7 Concurrent administration of warfarin.
- 3.2.8 Concurrent systemic immunosuppressant therapy within 21 days of the first dose of study drug.
- 3.2.9 Vaccinated with live, attenuated vaccines within 4 weeks of first dose of study drug.
- 3.2.10 Recent infection requiring systemic treatment that was completed \leq 14 days before the first dose of the study drug.
- 3.2.11 Known bleeding disorders (e.g., congenital von Willebrand's disease or hemophilia)
- 3.2.12 History of stroke or intracranial hemorrhage within 6 months prior to enrollment.
- 3.2.13 Major surgery within 4 weeks of first dose of study drug.

- 3.2.14 Malabsorption syndrome or other condition that precludes enteral route of administration.
- 3.2.15 Female participants who are pregnant, breastfeeding, or planning to become pregnant while enrolled in this study or within 90 days of last dose of study drug.
- 3.2.16 Male participants who plan to father a child while enrolled in this study or within 90 days after the last dose of study drug
- 3.2.17 Participants with known history of alcohol or drug abuse.
- 3.2.18 Participants with inability to swallow pills.
- 3.2.19 On any active therapy for other malignancies with the exception of topical therapies for basal cell or squamous cell cancers of the skin.

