5.4 General Concomitant Medication and Supportive Care Guidelines

Participants will be instructed not to take any additional medications (including over-the-counter products) during the course of the study without prior consultation with the investigator. At each visit, the investigator will ask the participant about any new medications he/she is or has taken after the start of the study drug.

Anti-emetics are permitted if clinically indicated. Standard supportive care medications are permitted. All Concomitant medications/Significant non-drug therapies taken ≤ 30 days prior to start and after start of study drug, including physical therapy and blood transfusions, should be recorded. The following restrictions apply during the entire duration of the study:

- No other investigational therapy should be given to participants.
- No anticancer agents other than the study medications should be given to participants. If such agents are required for a patient, then the patient must first be withdrawn from the study.
- Growth factors (i.e. G-CSF, GM-CSF, erythropoietin, platelets growth factors etc.) can be administered prophylactically, except for eligibility, and may be prescribed at the discretion of the treating physician for treatment-related hematologic events in accordance with ASCO guidelines, and to meet re-treatment criteria.
- Transfusions of red blood cells can be administered to meet eligibility and for treatment-related hematologic events in accordance with ASCO guidelines, and to meet re-treatment criteria.

- Transfusions of platelets can be administered for treatment-related hematologic events in accordance with ASCO guidelines, and to meet re-treatment criteria. They may not be administered to meet eligibility.
- Warfarin or vitamin K antagonists should not be administered.
- Participants requiring the initiation of therapeutic anticoagulation therapy (eg, atrial fibrillation), consider the risks and benefits of continuing ibrutinib treatment. If therapeutic anticoagulation is clinically indicated, treatment with ibrutinib should be held and not be restarted until the participant is clinically stable and has no signs of bleeding. Participants should be observed closely for signs and symptoms of bleeding. No dose reduction is required when study drug is restarted.

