Diarrhea is the most frequently reported non-hematologic AE with ibrutinib monotherapy and combination therapy. Other frequently reported gastrointestinal events include nausea, vomiting, and constipation. These events are rarely severe and are generally managed with supportive therapies including antidiarrheals and antiemetics. Subjects should be monitored carefully for gastrointestinal AEs and cautioned to maintain fluid intake to avoid dehydration. Medical evaluation should be made to rule out other etiologies such as *Clostridium difficile* or other infectious agents. Should symptoms be severe or prolonged follow the protocol dose modification guidelines (see Section 6).

Hypertension

Hypertension has been commonly reported in subjects treated with ibrutinib. Monitor subjects for new onset of hypertension or hypertension that is not adequately controlled after starting ibrutinib. Adjust existing anti-hypertensive medications and/or initiate anti-hypertensive treatment as appropriate.

Infections

Infections (including sepsis, bacterial, viral, or fungal infections) were observed in subjects treated with ibrutinib. Some of these infections have been associated with hospitalization and death. Consider prophylaxis according to standard of care in subjects who are at increased risk for opportunistic infections. Although causality has not been established, cases of progressive multifocal leukoencephalopathy (PML) and hepatitis B reactivation have occurred in subjects treated with ibrutinib. Subjects should be monitored for signs and symptoms (fever, chills, weakness, confusion, vomiting and jaundice) and appropriate therapy should be instituted as indicated.

Non-Melanoma Skin Cancer

Non-melanoma skin cancers have occurred in patients treated with ibrutinib. Monitor patients for the appearance of non-melanoma skin cancer.

Rash

Rash has been commonly reported in subjects treated with either single agent ibrutinib or in combination with chemotherapy. Most rashes were mild to moderate in severity. Isolated cases of severe cutaneous adverse reactions (SCARs) including Stevens-Johnson syndrome (SJS) have

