7.8.3 Other Malignancies

All new malignant tumors including solid tumors, skin malignancies and hematologic malignancies will be reported for the duration of study treatment and during any

protocol-specified follow-up periods including post-progression follow-up for overall survival. If observed, enter data in the corresponding eCRF.

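### The new-therapy event in progression and PFS is not limited to WM, so systemic treatment of an unrelated cancer reads as WM progression and ends disease follow-up

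*Combined protocol and SAP*

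**What the plan says.** The rule appears in two places. In Section 11.1.2 (Response Criteria), under progressive disease: "Death from any cause or initiation of a new anti-neoplastic therapy will also be considered a progression event". In Section 11.1.1 (Time-to-event definition), PFS runs from start of treatment to "time of objective disease progression (including initiation of new therapy or death"). Neither sentence names the disease being treated.

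Two further places tie follow-up to the same trigger. Section 5.6: "Participants will be followed for progression free survival until documented disease progression or initiation of new therapy", with survival follow-up only after that. Section 10, footnote 10: "After PD or new therapy initiation, participants will be followed for survival status only"; footnote 11 sets that survival contact at every 6 months.

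Other cancers are foreseen elsewhere. Section 7.8.3: "All new malignant tumors including solid tumors, skin malignancies and hematologic malignancies will be reported for the duration of study treatment", and this reporting extends through follow-up. Exclusion 3.2.19 bars entry for participants "On any active therapy for other malignancies with the exception of topical therapies for basal cell or squamous cell cancers of the skin". Section 5.4 says "No anticancer agents other than the study medications should be given to participants" and requires that a patient who needs such an agent first be withdrawn from the study.

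Section 13.6 analyses PFS by Kaplan-Meier at 24, 36, 48 and 60 months. Participants without an event are censored at the last relevant assessment. It has no separate provision for therapy directed at another cancer.

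**The concern.** Take two participants in VGPR with the same IgM, nodes and spleen. One starts systemic therapy for an unrelated cancer and the other does not. As written, the first has a WM progression event that day and the second is progression-free, although their WM status is identical.

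Two things are at stake. The long-term PFS landmarks would fall with each treated second cancer, so an outcome already collected under safety would also be read as loss of WM control. In addition, once the event is declared, scheduled disease assessment stops. Recoding the event at analysis would not restore the WM progression date, because the data would not have been collected. Follow-up continues for four years after the study-wide stop of treatment, so the affected period is still open under this version of the protocol.

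**Working it through.** **Does any other text supply the limit?**

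- Where the protocol wants a qualifier, it can write one. Exclusion 3.2.1 refers to earlier systemic treatment specifically for WM. The opening of Section 5 refers to therapy intended to treat the participant's own malignancy. Exclusion 3.2.19 deals separately with treatment of other malignancies.
- The progression and PFS sentences carry neither a WM qualifier nor an exception for other cancers.
- The censoring rule in Section 13.6 does not mention such therapy.

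So the literal reading stands: any new anti-neoplastic therapy counts.

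**What happens to later data?** Footnote 10 is attached to the laboratory and response rows of the calendar, not to the CT and marrow rows. Its own wording, footnote 11 and Section 5.6 nevertheless all leave survival status only.

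**Is the handling consistent?** Section 5.4 points to withdrawal before another anticancer agent is given. Section 5.6 and the footnotes keep the same person in survival follow-up, and Sections 11.1.2 and 11.1.1 count an event. Section 5.7 does not list such treatment among its off-study criteria. Section 5.3.1 has follow-up running to next therapy or death, again without naming the disease. One record could therefore be coded as an event or as a withdrawal.

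**Which endpoints are touched?**

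- PFS: directly, through both definitions.
- Duration of response: its definition ends at PD or death that is objectively documented and does not itself mention new therapy. It is affected only if the event in Section 11.1.2 is treated as documented PD.
- Primary VGPR rate: not affected. The rule of at least 19 of 50 gives an exact one-sided alpha of 0.0287 at 25% and power of 87.3% at 45%. These agree numerically with the stated 0.03 (labelled two-sided) and 87%, and the new-therapy event enters neither.

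**Direction.** Time to the earlier of a true PFS event and non-WM therapy cannot exceed time to the true PFS event. The change in PFS is therefore zero or downward.

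**Illustrative size.** The plan states no PFS target to reproduce. Every input here is an assumption: constant rate r of starting anti-neoplastic therapy for another cancer, independent of WM events and death.

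PFS as written(t) = true PFS(t) × exp(−r × t)

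Assume true 60-month PFS of 0.80. At a constant hazard, the true 24-month value is 0.80^(24/60) = 0.915.

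| r per year | 24 months | 60 months |
|---|---|---|
| 0 (true) | 91.5% | 80.0% |
| 1% | 89.6% | 0.80 × exp(−0.05) = 76.1% |
| 2% | 87.9% | 0.80 × exp(−0.10) = 72.4% |
| 4% | 84.4% | 0.80 × exp(−0.20) = 65.5% |

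A second set of assumptions, with 24-month PFS of 90% or 80% and r from 1% to 5% per year, gives these 48-month values:

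- From 90%: 0.90² = 81.0% falls to 77.8% at r = 1% and 66.3% at r = 5%.
- From 80%: 0.80² = 64.0% falls to 61.5% at r = 1% and 52.4% at r = 5%.

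The loss runs from 64.0 − 61.5 = 2.5 points to 81.0 − 66.3 = 14.7 points.

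If people treated for a second cancer are also more likely to die or progress soon afterwards, part of this loss would have occurred anyway. The independence assumption then overstates it.

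**The case against.** The strongest reply is context. The sentence sits inside a WM progression definition, under WM response criteria, and time to next treatment is listed beside PFS. The authors may well have meant WM therapy. That is plausible, but it leaves a missing qualifier that sites can resolve differently, and the follow-up rules act on whichever reading a site adopts.

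Second, this PFS already counts death from any cause, so it is a broad composite. Counting new therapy is also conservative, since treatment for another cancer may act on WM. Event, censoring and continued follow-up are all defensible choices. This has weight, and it is why the fix includes a censoring analysis. It does not justify labelling the event WM progression or stopping collection of the data needed to compare the choices.

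Third, the endpoints are secondary, single-arm and untested, and second malignancies are recorded, so affected participants could be identified. That limits the consequence. It does not recover their later WM assessments.

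A reader might go further and infer that a topical agent for a skin cancer counts as progression, especially as Section 7.1.1.2 notes "Non-melanoma skin cancers have occurred in patients treated with ibrutinib". The documents do not support stating this. Anti-neoplastic therapy is undefined and could be read as systemic only. The one place that mentions topical skin-cancer treatment exempts it, though only for eligibility. The point rests on systemic therapy alone.

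**Conclusion.** The point holds as a defect of definition. As written, systemic treatment of an unrelated cancer is a PFS event and ends WM assessment, and no other section prevents this. The bias in the 24- to 60-month PFS can only be downward.

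Its size cannot be set from the documents, which give neither a rate of second-cancer treatment nor an expected PFS. The 60-month range of about 76% to 66% against 80% depends wholly on the assumed 1% to 4% per year, the assumed 80%, constant hazards and independence.

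Two stronger readings should be avoided. A reader might turn the rates into a number of false events among the planned 50 participants. Accrual was permanently discontinued and the documents give no enrolled number, so such a count has no base. A reader might also state that duration of response is biased; that is conditional on how documented PD is read. Nothing here bears on the primary VGPR analysis.

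**What to change.** 1. In Section 11.1.2 and in the PFS definition in Section 11.1.1, limit the event to new anti-neoplastic therapy for WM, including transformed disease.
2. Use the same words in Section 5.6, in study calendar footnotes 10 and 11, and in Section 5.3.1 where follow-up is said to run until next therapy.
3. State that treatment of another malignancy is not in itself a progression event and that scheduled WM assessments continue in follow-up.
4. Reconcile this with Section 5.4, which calls for withdrawal before another anticancer agent is given. The sponsor should settle how the two fit together so that one record cannot be coded in two ways.
5. Add one sensitivity analysis of PFS that censors at the start of systemic therapy for another cancer.

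The cost is a consistent wording change in six places (Sections 11.1.2, 11.1.1, 5.6 and 5.3.1, and footnotes 10 and 11), the reconciliation of Section 5.4, and continued scheduled assessments for what is likely to be a few participants. The small downside is that therapy for another cancer may also suppress IgM and delay apparent WM progression; the sensitivity analysis addresses this. The change needs to be made while follow-up is open, because assessments not done cannot be recovered.
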